**NCT 02648698**

**Date: May 30, 2020**

## study protocol

### Background

Chronic endometritis (CE) is a condition characterized by the presence of plasma cell in the endometrial stroma. CE may be associated with abnormal uterine bleeding, intrauterine pathology such as polyp or fibroid, as well as a variety of reproductive failure including infertility, recurrent implantation failure and recurrent pregnancy loss. In women with reproductive failure, the reported prevalence of CE maybe as high as 41%.

CE is often treated with antibiotics on the assumption that it is caused by an underlying infection. The response of CE to antibiotic therapy has been examined in a number of cohort studies. The cure rate, as determined by reduction of plasma cell density in a repeat endometrial biopsy specimen following antibiotic therapy was found to be 75.4%, 99% and 100%.

The impact of antibiotic therapy on clinical outcome among subjects with CE had also been examined in several cohort studies. Cicinelli et al conducted a retrospective study which showed that after antibiotic therapy, the pregnancy rate (PR) and live birth rate (LBR) in women who become CE negative was higher than those who remained CE positive after antibiotic treatment (65.2% versus 33.0% ; 60.8% versus 13.3%, respectively) . In another study involving women with recurrent implantation failure (RIF) study, Kitaya et al. reported that the LBR in the first embryo transform (ET) cycle and cumulative three ET cycles in the cured CE group following antibiotic treatment (32.8% and 38.8%, respectively) was significantly higher than those of the non-CE group (22.1% and 27.9%, respectively). McQueen et al observed that the cumulative LBR was 88% (21/24) for the treated CE group versus 74% (180/244) for the group without CE. In the CE group, the LBR for those before treatment was 7% (7/98) versus 56% (28/50) after treatment.

Despite the apparently encouraging clinical data from the above observational, cohort studies suggesting that antibiotic treatment was effective in curing CE and

improving the reproductive outcome, the impact of antibiotic therapy has not yet been formally examined in any randomized control trial.

### **Objective**

To compare the cure rate of chronic endometritis between subjects who did and did not receive antibiotic treatment.

[figure not shown]
### **Design**

Prospective, Single-blind randomized, controlled trial.

This RCT was conducted in the Hysteroscopic Centre, Fuxing Hospital, Capital Medical University, a national training centre for hysteroscopy in China between 2016 and 2018. During the period of study, women who were referred to the center for hysteroscopy for investigation of reproductive failure including infertility, recurrent miscarriage (RM) or recurrent implantation failure (RIF), as well as abnormal menstruation had endometrial biopsy obtained for histological examination including CD138 immunohistochemical staining as a routine procedure.

The inclusion criteria for patient participation in this study included: (1) CD138 immunohistochemical staining of endometrial specimen showed presence of one or more plasma cells per 10HPF which confirmed chronic endometritis, according to published criteria; (2) women who were pre-menopausal; (3) no evidence of endometrial hyperplasia or malignancy or structural uterine pathology; (4) agreement to have a second endometrial biopsy ~4 weeks after the initial endometrial biopsy; and (5) written informed consent obtained.

The exclusion criteria included: (1) women who received steroid hormone therapy within one month of recruitment; (2) allergy or suspected allergy to the chosen antibiotic therapy; (3) women who developed any concurrent infection and received any antibiotic therapy during the period of study other than the one prescribed according to the study protocol.

A total of 120 subjects were randomized in antibiotic group and control group in a 1:1 ratio using a computer-generated randomization list, 6 subjects did not attend for second hysteroscopy and endometrial biopsy. At the end, 59 subjects in the antibiotic group and 55 subjects in the control group completed the study according to the protocol, these 114 cases were included in the final analysis.

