**Methods**

Women randomized to antibiotic group received oral Levofloxacin 500 mg and Tinidazole 1000 mg daily for 14 days. Women randomized to the control group did not receive any treatment. Initially it was planned for women in the control group to take placebo, but the organization was difficult, so it was changed prior to the start of

the study to an open label study. A repeat endometrial biopsy was performed 4-8 weeks after the initial biopsy to determine if CE was still present.

The conversion rate of CE (from positive to negative) in two group were compared.

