### **statistical analysis plan**

The comparison of results between the two groups was made with the use of an independent-sample t-test for continuous variables and contingency table analysis for categorical variables. A P value of  $<.05$  was considered to be significant. All statistical tests were two sided. Statistical analysis was performed with the use of SPSS for PC version 21(2016).

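### Does an exclusion criterion that can be met after randomisation bias the comparison of conversion rates?

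*Combined protocol and SAP*

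**What the plan says.** The Design section lists three exclusion criteria. The first, on steroid hormone use, is tied to recruitment. The third has no such anchor: it covers "women who developed any concurrent infection and received any antibiotic therapy during the period of study other than the one prescribed" under the protocol.

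The same section gives the flow of participants: "A total of 120 subjects were randomized in antibiotic group and control group in a 1:1 ratio using a computer-generated randomization list", then "6 subjects did not attend for second hysteroscopy and endometrial biopsy", then "59 subjects in the antibiotic group and 55 subjects in the control group completed the study according to the protocol". Those women form the set analysed.

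The Methods section sets the time over which the third criterion could operate: "A repeat endometrial biopsy was performed 4-8 weeks after the initial biopsy to determine if CE was still present". It also says that controls received no treatment and that the study became open label before it started.

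The statistical analysis plan names a t-test for continuous variables and "contingency table analysis for categorical variables", with the significance level, two-sided testing and the software. It defines no intention-to-treat or per-protocol set, and it has no rule for a randomised woman who later meets an exclusion criterion.

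**The concern.** An eligibility criterion should be settled before allocation. This one describes an infection and a course of outside antibiotics, and both can occur between randomisation and the repeat biopsy. The exception for study antibiotics also makes most sense once treatment has been assigned.

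If the criterion were applied at that stage, it would take randomised women out of the comparison for something that might differ between the arms. One arm takes two antibiotics for 14 days; the other takes nothing and, without a placebo, can know it. Outside antibiotic use could also bear directly on the endpoint, since the trial asks whether antibiotics clear chronic endometritis. The analysed women would then no longer be the groups that randomisation created, and the difference in conversion rates could move either way. The documents give no infection or outside-antibiotic rates by arm, so no direction can be assigned.

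Nothing in the analysis plan counters this, and describing the analysed women as having completed according to the protocol leans towards removal.

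**Working it through.** **Inputs, all from the Design section**

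- Randomised: 120, in a 1:1 ratio (numbers per arm not stated).
- Did not attend for the second biopsy: 6 (split by arm not stated).
- Analysed: 59 antibiotic, 55 control.

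**Step 1: reproduce the number analysed**

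59 + 55 = 114, and 120 - 6 = 114. The two agree with the stated 114.

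**Step 2: solve for removals under the third criterion**

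Let k be the number of women removed under this criterion, counted apart from the non-attenders:

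analysed = randomised - non-attenders - k

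114 = 120 - 6 - k, so k = 0.

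One removal would leave 120 - 6 - 1 = 113 analysed. Five would leave 120 - 6 - 5 = 109. Neither matches 114.

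**Step 3: how far removals could move an arm's conversion rate**

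Suppose an arm has n women, k are removed, the remaining n - k convert at rate r, and c of the k removed would have converted (c between 0 and k). Then:

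- rate with the criterion applied = r
- rate as randomised = [r(n - k) + c] / n
- shift = r - [r(n - k) + c] / n = (k/n)(r - c/k), for k above zero

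The shift can take either sign and cannot exceed k/n in size. With n = 60 (an assumption, since the arm sizes are not given), each woman removed could move her arm's rate by at most 1/60 = 1.7 percentage points. With k = 0 the two rates are the same and the shift is zero.

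**Step 4: what k = 0 allows**

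For women with a second biopsy, two readings fit the flow: none met the criterion, or some did and were analysed anyway. Neither is an exclusion after randomisation. In the second case, outside antibiotics might dilute the contrast, but the groups are still those that were randomised.

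A woman who met the criterion could be among the 6. Those 6 are described as having no second biopsy, so no rule about analysing women with a result would bring them back.

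**Step 5: keep the 6 losses separate**

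If exactly 60 were randomised to each arm (an assumption), the losses are 60 - 59 = 1 (1/60 = 1.7%) on antibiotics and 60 - 55 = 5 (5/60 = 8.3%) in controls; Fisher's exact p = 0.21. Splits that fit the totals run from 0 of 59 and 6 of 61 to 6 of 65 and 0 of 55. This is a question about missing outcomes. The stated reason is non-attendance, so the losses are not evidence that the third criterion was applied.

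**The case for a change.** The best argument for a change is that arithmetic on a reported flow does not replace a rule. The criterion is listed as a ground for exclusion, the analysis plan does not say whom to analyse, and the text reports no count of women who took outside antibiotics. If 120 were a net figure, reached after some women had been removed or replaced, the balance in the flow would hide the problem. One sentence on the analysis set and one count per arm would settle the matter at almost no cost.

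Part of this stands. The criterion does reach past randomisation, the analysis plan has no analysis-set definition, and the text gives no count by arm of women who met the criterion.

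The rest does not carry a change. The document presents 120 as the number randomised, and a woman removed after allocation belongs in that number on its ordinary meaning. Replacement is not mentioned anywhere, so treating 120 as a net figure is conjecture. Scenarios in which several women are removed from one arm contradict the stated totals. A figure under the Objective heading is not reproduced in the available text; it may or may not show participant flow, so the lack of a count cannot safely be held against the plan. Rewording the criterion now would also rewrite an eligibility rule after recruitment had ended, since the trial ran between 2016 and 2018 and the document is dated May 2020.

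**Conclusion.** The wording is weak, but it has no shown consequence. On the stated flow, the number of women removed under the third exclusion criterion is zero, and so is the resulting shift in either arm's conversion rate. Keeping women who met it after randomisation in their assigned groups would give the same 114 women, 59 against 55, and the same result.

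This rests on two readings of the Design section: that 120 is everyone randomised, and that the 6 losses are non-attenders, as stated. It does not show that no woman took outside antibiotics; it shows that none with a second biopsy was dropped for doing so. What remains is missing detail about the analysis set, which analysts would ordinarily fill by analysing each woman with a second biopsy in the arm to which she was allocated. A count by arm of women who met the criterion would be a useful line in a trial report, but it would not alter the comparison. No change to the plan follows.

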**Methods**

Women randomized to antibiotic group received oral Levofloxacin 500 mg and Tinidazole 1000 mg daily for 14 days. Women randomized to the control group did not receive any treatment. Initially it was planned for women in the control group to take placebo, but the organization was difficult, so it was changed prior to the start of

the study to an open label study. A repeat endometrial biopsy was performed 4-8 weeks after the initial biopsy to determine if CE was still present.

The conversion rate of CE (from positive to negative) in two group were compared.

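### Does the loosely stated timing of the repeat biopsy (about 4 weeks in one place, 4 to 8 weeks in another) undermine the cure-rate comparison?

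*Combined protocol and SAP*

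**What the plan says.** Two places give the timing of the second biopsy. In the Design section, inclusion criterion 4 requires "agreement to have a second endometrial biopsy ~4 weeks after the initial endometrial biopsy". The Methods section reports: "A repeat endometrial biopsy was performed 4-8 weeks after the initial biopsy to determine if CE was still present". Only one repeat biopsy is described, and the outcome is read from it: "The conversion rate of CE (from positive to negative) in two group were compared".

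The Design section describes the analysed women as those who "completed the study according to the protocol, these 114 cases were included in the final analysis". On treatment, the Methods section states: "Women randomized to antibiotic group received oral Levofloxacin 500 mg and Tinidazole 1000 mg daily for 14 days". The control arm took nothing. A planned placebo was given up before the start, which changed "the study to an open label study".

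The SAP gives an independent-samples t-test for continuous variables and "contingency table analysis for categorical variables", two-sided at the 5% level. It does not name the biopsy interval.

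**The concern.** A biopsy at 6 to 8 weeks fits the Methods section but is hard to call about 4 weeks. A reader may therefore ask to what time the cure rate applies, and whether timing decided who counted as having completed per protocol.

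The more serious worry is bias. If some untreated women clear their plasma cells spontaneously, conversion rises with time since the first biopsy. The second biopsy is dated after randomisation, allocation is known, and only one arm takes a 14-day course, so the interval could drift apart between arms. A plain contingency table of conversion by arm would not reveal this. Later biopsies in the antibiotic arm would flatter the antibiotic; later biopsies in the control arm would count against it.

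**Working it through.** **1. The two statements side by side.** Both count from the initial biopsy, so the origin is the same in both arms. One is 28 days, given as approximate and without a window; the other is 28 to 56 days. The first lies inside the second. The first is something women agreed to at entry; the second, in the past tense, says when the biopsy took place. An approximate target with a wider achieved range is a natural reading, although the text does not spell it out.

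**2. The analysed set (Design section).** Randomised: 120. Did not attend the second biopsy: 6. Then 120 − 6 = 114, and 59 + 55 = 114. Non-attendance accounts for every missing woman, so no attender was dropped because of when she was biopsied.

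**3. Size of the bias if one arm were later.** The documents give neither a spontaneous clearance rate nor intervals by arm, so the following are assumptions: a constant untreated clearance q per 4 weeks with q = 10%, 20% or 30%, no drug effect, one arm biopsied at 4 weeks and the other later. Untreated conversion by week t is 1 − (1 − q)^(t/4). The chance of P<.05 comes from exact binomial enumeration of the uncorrected two-sided chi-square test with 59 antibiotic and 55 control women.

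| | q = 10% | q = 20% | q = 30% |
|---|---|---|---|
| Conversion at 4 weeks | 10.0% | 20.0% | 30.0% |
| Conversion at 5 weeks | 12.3% | 24.3% | 36.0% |
| Conversion at 6 weeks | 14.6% | 28.4% | 41.4% |
| False difference, one week (points) | 2.3 | 4.3 | 6.0 |
| False difference, two weeks (points) | 4.6 | 8.4 | 11.4 |
| P<.05, equal timing at 4 weeks | 5.1% | 5.1% | 5.0% |
| P<.05, antibiotic one week later | 6.5% | 8.8% | 10.4% |
| P<.05, antibiotic two weeks later | 11.0% | 18.7% | 24.6% |
| P<.05, control two weeks later | 12.3% | 18.0% | 25.2% |

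In the last row nearly all the significant results go against the antibiotic. For scale, these arm sizes give 80% power only for a true difference of about 21 to 26 points at these control rates.

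**4. The wide window itself.** Now let both arms be spread evenly over 4 to 8 weeks. Mean conversion is 1 − q(1 − q)/(−ln(1 − q)):
- q = 10%: 1 − 0.09/0.1054 = 14.6%
- q = 20%: 1 − 0.16/0.2231 = 28.3%
- q = 30%: 1 − 0.21/0.3567 = 41.1%

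The rate is the same in both arms, and the chance of P<.05 is 5.1%, 5.0% and 5.1%. A broad window alone produces no bias; only a difference between arms does.

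**5. With a drug effect.** The Background says the cohort cure rate "was found to be 75.4%, 99% and 100" percent. Take 75% conversion on the antibiotic, rounded from the lowest of these and still an assumption for this trial.
- Antibiotic arm later: only the remaining 25% can still clear, so the shift is 0.25 × (1 − (1 − q)^(1/4)) = 0.6, 1.4 or 2.1 points for one week, and 0.25 × (1 − (1 − q)^(2/4)) = 1.3, 2.6 or 4.1 points for two.
- Control arm two weeks later: the comparison is 75% against 14.6%, 28.4% or 41.4%, and power is above 99.9%, above 99.9% and 96%.

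**The case for a change.** The strongest case for a change is that this biopsy is the only outcome assessment, that the two stated upper limits differ by a factor of two, and that nothing in the SAP commits the analyst to look at the interval. Allocation was known and only one arm was treated, so a check by arm is a fair thing to want. It would cost little: a table row, and perhaps a logistic model of conversion on arm and interval as a sensitivity analysis.

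Part of this stands. The time to which the cure rate applies is loosely stated, and the two sections should be reconciled to the window that was applied; this review does not say which timing is right. If biopsy dates were recorded, which the documents do not say, a median and range of the interval by arm would help the reader. The SAP's t-test clause for continuous variables could already be applied to the interval, though the plan does not say so.

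The rest does not carry. Stating the window and tabulating the interval describe what was done and alter no estimate or test. The model would condition on a variable fixed after randomisation, so it can introduce bias of its own. It would also be post hoc, since the trial ran from 2016 to 2018 and the document is dated 2020. It would replace no weakness that has been shown.

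**Conclusion.** The difference in wording is real but minor, and it calls for no change to the plan. The two timings overlap, they count from the same origin, and the analysed set closes exactly at 114.

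The bias is a possibility only. The documents show no interval difference between arms and give no reason to expect one in a particular direction. A false-positive rate of 11% to 25% would need a two-week delay across a whole arm, constant spontaneous clearance of 10% to 30% per 4 weeks, and no drug effect at all, none of which comes from the documents. With timing balanced across the window, the rate is 5.0% to 5.1%.

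The conclusion rests on the interval having been similar in the two arms. The documents neither show this nor give cause to doubt it. On that footing the unadjusted contingency-table comparison of the randomised arms is sound as written, and adjusting it for the interval would be a trade-off without clear gain.

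### The conversion comparison makes no use of the starting plasma-cell count; the crude test stays valid but loses precision and protection against chance imbalance

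*Combined protocol and SAP*

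**What the plan says.** - **Entry (Design, inclusion criterion 1).** A woman qualifies if "CD138 immunohistochemical staining of endometrial specimen showed presence of one or more plasma cells per 10HPF". This is a floor only; no upper limit or density band is given.
- **Allocation (Design).** Women were allocated "in a 1:1 ratio using a computer-generated randomization list". No stratification factor is named.
- **Outcome (Methods).** "The conversion rate of CE (from positive to negative) in two group were compared". Each woman counts as converted or not on the repeat biopsy.
- **Analysis (statistical analysis plan).** The method for this outcome is "contingency table analysis for categorical variables", two-sided at the 5% level. No covariate, stratified, subgroup or sensitivity analysis is mentioned.

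The documents do not give the mix of starting counts, conversion by starting count, or an expected conversion rate without treatment. They also do not say whether a numerical count, rather than a positive reading, was kept for each woman.

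**The concern.** A woman with one plasma cell per 10HPF and a woman with many enter as the same positive case. If a negative reading means falling below the entry threshold, the first woman is closer to it before anything is done. The Background also describes cure in earlier cohorts as a fall in plasma-cell density. The starting count is therefore a natural candidate for a baseline predictor, and it comes from the same stain that decides eligibility.

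The untreated arm is there to show how often conversion happens without antibiotics. With 59 and 55 women analysed, the arms can differ noticeably by chance in their share of low-count women, and a crude table has no means of allowing for that. At stake are the width of the confidence interval and how far this one realised estimate can be trusted. No sample size or power justification is given, so spare precision cannot be assumed.

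**Working it through.** **Inputs from the documents.** 120 randomised, 6 without a second biopsy, 59 and 55 analysed, two-sided 5% test. The one figure that can be reproduced is the analysis set: 120 − 6 = 114 = 59 + 55.

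**Assumptions (not in the documents).** Half the women are low-density (q = 0.5). Untreated conversion differs by a gap g between low and high density. Any treatment effect is additive.

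**Is a gap plausible?** Suppose the count on re-biopsy is Poisson with no true change. The chance of seeing zero cells is exp(−mean): 37% at a mean of 1, 5% at 3 and 0.7% at 5. Sampling variation alone could then make low-count women appear to convert. This supports plausibility only; the Poisson model is itself an assumption.

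**Chance imbalance.** The SD of the between-arm difference in low-density share is √[q(1−q)(1/59 + 1/55)] = √(0.25 × 0.03513) = 0.094, or 9.4 points. In simulation the arms differ by more than 10 points, in either direction, in about 30% of randomisations, so about 15% each way.

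**Shift in the crude difference.** This is imbalance × g. A 1-SD imbalance gives 9.4 × 0.20 = 1.9 points for a 20-point gap and 9.4 × 0.40 ≈ 3.7 points for a 40-point gap. Averaged over all randomisations the shift is zero.

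**Precision, one case by hand.** Take untreated conversion of 60% (low) and 15% (high) with a +30-point effect. The arm rates are 0.375 (control) and 0.675 (antibiotic).
- Crude variance: 0.675 × 0.325/59 + 0.375 × 0.625/55 = 0.00372 + 0.00426 = 0.00798, SD 8.9 points.
- Part due to the density mix: q(1−q)g²(1/59 + 1/55) = 0.25 × 0.2025 × 0.03513 = 0.00178.
- Share removable by stratifying: 0.00178/0.00798 = 22%. Simulation gives 21%, slightly less because the strata are finite.

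**Simulated results**, crude against Mantel-Haenszel risk difference with two strata (40,000 trials per scenario for the +30 and +20 rows, 200,000 for the others):

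| Untreated low/high | Effect (points) | SD crude (points) | SD stratified (points) | Variance cut |
|---|---|---|---|---|
| 30/30% | 0 | 8.6 | 8.6 | none |
| 30/10% | +25 | 8.4 | 8.3 | 4% |
| 50/25% | +30 | 8.9 | 8.7 | 6% |
| 60/20% | +25 | 9.1 | 8.3 | 16% |
| 50/10% | +25 | 9.0 | 8.2 | 17% |
| 60/15% | +30 | 8.9 | 7.9 | 21% |
| 70/10% | +20 | 9.2 | 7.3 | 36% |

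The cuts are taken from SDs before rounding to one decimal. Power for a 25-point effect rises from 82.6% to 84.1% (30/10%), 77.5% to 85.1% (50/10%) and 77.4% to 84.1% (60/20%).

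**Validity of the crude test.** With no treatment effect, two-sided type I error is 4.9-5.1% crude and 4.9-5.0% stratified. Given an imbalance above 15 points favouring the antibiotic arm, crude rejection rises to 7.9% (30/10%) or 11.6% (50/10%). Imbalances above 15 points in either direction occur in about 11% of trials.

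**The case against.** The strongest reply is that every unadjusted randomised comparison carries chance imbalance, and the 5% test already allows for it. That is right. A reader might infer that the crude conversion difference is biased or its P value invalid. The documents do not support that: allocation was randomised, the mean shift is zero and the error rate is about 5%. The rejection rates of 7.9% and 11.6% hold only after a large imbalance in one direction, and nothing in the documents shows that one occurred.

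Second, the link between starting count and conversion is not in the documents. This also stands. The shared scale makes it plausible, but every magnitude above is assumed, modest gradients gain little, and a flat one gains nothing.

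Third, a numerical count may not have been kept; the eligibility rule needs only a threshold reading. That limits how far the adjustment can be carried out.

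Fourth, the document is dated May 30, 2020, describes a trial run between 2016 and 2018, and reports 114 women in the final analysis. Replacing the stated comparison now would add analyst freedom after the data exist. This is a good reason to add the adjusted result beside the crude one rather than put it in its place.

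Fifth, the 59 and 55 are completers. If 60 were allocated to each arm (an assumption from the 1:1 ratio), 1 and 5 were lost. Imbalance from that source is not chance.

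None of this removes the precision argument.

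**Conclusion.** The point holds as a matter of efficiency and of protection for the realised trial. Entry has a floor but no density band, no stratified allocation is described, and the count is absent from the comparison. With half the women assumed low-density, adjustment would cut the variance of the difference by:

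- about 4-6% for untreated conversion of 30/10% or 50/25%;
- 16-21% for 50/10%, 60/20% or 60/15%;
- about 36% for 70/10%;
- essentially nothing with no gradient.

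A reader might also infer that the result applies only to women with minimal disease who clear untreated. The documents give neither the density mix nor any untreated clearance rate, and the Objective is an overall comparison of cure rates, so that inference is unsupported.

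**What to change.** Keep the endpoint and the crude table, and make two additions.

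1. Tabulate the initial plasma-cell count by arm.
2. Report one conversion difference adjusted for initial count: a Mantel-Haenszel risk difference with two strata cut at the pooled median, the cut set without reference to outcome. Place women with no recorded count in a separate missing category, not in the lowest stratum.

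Label the adjusted result post hoc if it was specified after outcomes were seen.

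The cost is a table, one further analysis and a sentence in the plan, with no new patients or procedures. Counts must be retrieved from pathology reports and may not exist for every woman. Adjustment would not fully correct imbalance arising from the 6 women who did not attend for the second biopsy.
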